#### **10.1.2 Cohort Expansion (Part 3)**

The sample size for Cohort 1 and 2 is up to 40 participants per cohort. Cohort 3 will treat up to approximately 12 evaluable participants.

Sample size calculations for Cohorts 1 and 2 assume the following:

- Assumes response rates below 6% and 20% for the low CD8 and mid CD8 cohorts, respectively, would not warrant further study. These are the approximate response rates in CA209275 participants with  $CD8 < 2\%$  and  $2\% \leq CD8 < 20\%$ , respectively.
- Assumes 2 or more indications per cohort.
- Assumes the treatment effect is the same across indications within a cohort.
- The nominal error rates are controlled at one-sided  $\alpha = 0.10$  and  $\beta = 0.20$ , but the actual power and type I error are shown in the tables below ([Table 10.1.2.1-1](#) and [Table 10.1.2.2-1](#)), which accounts for the discrete nature of the binomial distribution.

### 10.1.2.1 Cohort 1 (CD8 < 2%)

Assuming a 6% response rate for nivolumab monotherapy, the interesting rate for the combination therapy is 20%, then 35 participants are needed to detect at least 14.3% response rate.

Table 10.1.2.1-1: Power Estimates and Type 1 Error for Cohort 1			
		Historical Rate	
	X, N (alpha, power)	0.05	0.06
Target Rate	0.15	6, 55 (0.056, 0.852)	8, 72 (0.066, 0.864)
	0.2	4, 28 (0.049, 0.840)	5, 35 (0.056, 0.857)
X is the minimum # of responders to show not futile			

### 10.1.2.2 Cohort 2 (2% ≤ CD8 < 20%)

Assuming a 20% response rate for nivolumab monotherapy, the interesting rate for the combination therapy is 40%, then 33 participants are needed to detect at least a 33% response rate.

Table 10.1.2.2-1: Power Estimates and Type 1 Error for Cohort 2			
		Historical Rate	
	X, N (alpha, power)	0.15	0.2
Target Rate	0.3	12, 49 (0.055, 0.841)	31, 121 (0.079, 0.876)
	0.35	8, 29 (0.059, 0.849)	16, 57 (0.091, 0.893)
	0.4	6, 19 (0.054, 0.837)	11, 33 (0.051, 0.831)
X is the minimum # of responders to show not futile			

### 10.1.2.3 Cohort 3 (≥ 20%)

Cohort 3 is a monotherapy expansion of BMS-986277 which will treat participants with high CD8 TILs (≥20%) to further characterize the pharmacodynamics of BMS- 986277 alone at RD from Part 1. Up to 12 participants evaluable for pharmacodynamic endpoints will be treated in this cohort. Approximately 20% additional participants may be enrolled in this cohort to ensure the number of evaluable participants is achieved. To assess the PD effects, assuming that a biomarker

is measured as a continuous variable, 12 evaluable participants will provide the confidence that the estimate of the ratio of on-treatment biomarker values to baseline values will be within 20% of the true value as shown in Table 10.1.2.3-1.

**Table 10.1.2.3-1: Probability that Estimated Ratio of On-treatment to Pre-treatment (Baseline) Value is Within 20% of True Value**

Intra-subject Standard Deviation (Log-scale)	0.2	0.3	0.4	0.5	0.6	0.7	0.8
N = 12	99%	90%	78%	68%	59%	52%	46%

For example, for a biomarker with an intra-subject standard deviation of 0.5 on the log-scale, if the true ratio of on-treatment to baseline value geometric means is 1.2 (20% increase from baseline), there is a 68% probability that the estimated ratio is within 0.96 to 1.44 (a percent change from -4% to 44% from baseline) with 12 evaluable participants. If the true ratio is 1.3 (30% increase from baseline), with the same variability, there is a 68% probability that the estimated ratio is within 1.04 to 1.56 (a percent change from 4% to 56% from baseline).

## 10.2 Populations for Analyses

For purposes of analysis, the following populations are defined:

Population	Description
Enrolled	All participants who sign informed consent and are registered into the IRT
Treated	All participants who take at least 1 dose of study treatment
Response-evaluable	All treated participants with measurable disease at baseline and 1 of the following: (a) at least 1 post baseline tumor assessment, (b) clinical progression, or (3) death
Pharmacokinetic	All treated participants who have evaluable concentration-time data
Immunogenicity	All treated participants who have a baseline and at least 1 post baseline immunogenicity assessment
Biomarker	All treated participants with evaluable biomarker data for the specific analysis

## 10.3 Statistical Analyses

Final analysis will be performed after all participants are enrolled and have been followed for the minimum time to evaluate the primary endpoint. The statistical analysis plan will be developed and finalized before the database lock for the final analysis. Below is a summary of planned statistical analyses of the primary and secondary endpoints, and select exploratory endpoints. In general, summaries will be performed by dose level, cohort, and indication. If sufficient data are not available such that adequate interpretation of the result is not warranted, some summaries may not be performed and only listings will be presented.

A description of the participant population will be included in a statistical output report, including subgroups of age, gender and race.

### 10.3.1 Efficacy Analyses

The primary efficacy analyses (see Table below) will be performed on the treated population for the final analysis. Efficacy analyses based on the response-evaluable population may be performed for interim analyses when the minimum follow-up period is less than sufficient to warrant adequate interpretation of the result. Efficacy analyses will be performed using the RECIST v1.1 (all indications except prostate) or PCWG3 criteria (prostate), and may be repeated by BICR using iRECIST (all except prostate), if data permits. Details of the censoring scheme on time-to-event endpoints such as DOR (all except prostate), PFS, OS, immune DOR (iDOR), and immune PFS (iPFS) will be described in the Statistical Analysis Plan.

Endpoint	Statistical Analysis Methods
ORR is defined as the proportion of all treated participants whose BOR is either CR or PR. DCR includes CR, PR, and SD. BOR for a participant will be assessed per RECIST v1.1 or PCWG3 by BICR and/or by investigator, where available.	Estimate of ORR and DCR and corresponding 2-sided exact 95% CI using the Clopper-Pearson method
mDOR DOR for a participant with a BOR of CR or PR is defined as the time between the date of first response and the date of the first objectively documented tumor progression per RECIST v1.1/PCWG3 or death, whichever occurs first.	Estimate by the Kaplan-Meier method and corresponding 2-sided 95% CI using Brookmeyer and Crowley methodology (using log-log transformation)
mPFS and PFSR at 8, 16, and 24 weeks PFS for a participant is defined as the time from the first dosing date to the date of first objectively documented disease progression or death due to any cause, whichever occurs first	Estimate by the Kaplan-Meier method and corresponding 2-sided 95% CI using Brookmeyer and Crowley methodology (using log-log transformation) for the median and Greenwood formula for the rate
mOS and OSR at 3, 6, 9, and 12 months OS for a participant is defined as the time from the first dosing date to the date of death for any cause	Estimate by the Kaplan-Meier method and corresponding 2-sided 95% CI using Brookmeyer and Crowley methodology (using log-log transformation) for the median and Greenwood formula for the rate
Summary measures of indication-specific efficacy biomarkers, such as absolute PSA and PSA doubling time (prostate), CEA (colorectal), Ca125 (ovarian), and Ca19-9 (pancreatic)	Summary statistics/plots by visit Spider plots

Abbreviations: BICR = blinded independent central review; BOR = best overall response; CI = confidence interval; CR = complete response; DCR = disease control rate; DOR = duration of response; iRECIST = immune Response Evaluation Criteria In Solid Tumors; mDOR = median duration of response; mOS = median overall survival; mPFS = median progression-free survival; ORR = objective response rate; OS = overall survival; OSR = overall survival rate; PCWG = Prostate Cancer Working Group; PFS = progression-free survival; PFSR = progression-free survival rate; PR = partial response; RECIST = Response Evaluation Criteria in Solid Tumors, SD = stable disease

### 10.3.2 Safety Analyses

All safety analyses will be performed on the treated population.

Endpoint	Statistical Analysis Methods
Incidence of AEs, SAEs, AEs meeting protocol-defined DLT criteria, AEs leading to discontinuation, AEs resulting in death, and deaths AEs will be graded according to CTCAE v4.03	DLT rate by dose level; frequency distribution of treated participants with AE using the worst CTC grade. Participants will only be counted (1) once at the PT level, (2) once at the SOC level, and (3) once in the “total participant” row at their worst CTC grade, regardless of SOC or PT.
Incidence of clinical laboratory test abnormalities Laboratory values will be graded according to CTCAE v4.03	Laboratory shift table using the worst CTC grade on treatment per participant
Vital sign abnormalities or other safety biomarkers	Summary tables of vital signs Frequency statistics of renal function and bladder hemorrhage

Abbreviations: AE = adverse event; CTC = common terminology criteria; CTCAE = common terminology criteria for adverse events; DLT = dose-limiting toxicity; PT = preferred term; SAE = serious adverse event; SOC = system organ class

### 10.3.3 Pharmacokinetic Analyses

All PK analyses will be performed on the PK population. Each endpoint will be summarized for BMS-986277 and nivolumab separately, where available. Refer to [Section 9.5](#) for the definition of the PK parameters.

Endpoint	Statistical Analysis Methods
C max , AUC(0-T), AUC(0-8), AUC(0-48), AUC(INF), T-HALF, CLT, V ss , V z , C 48 , C ss-avg , AI_AUC, AI_C max , and T-HALF eff	Summary statistics: geometric means and coefficients of variation
C max , AUC(0-T), AUC(0-8), AUC(0-48)	Scatter plots versus dose for each cycle measured; dose proportionality based on a power model and a CI around the power coefficient
T max	Summary statistics: medians and ranges
C trough	Summary statistics to assess attainment of steady state: geometric means and coefficients of variation, by treatment and by day, plots versus time by dose

Abbreviations: AI = accumulation index; AUC = area under the concentration-time curve; C48 = plasma concentration 48 hours postdose; CLT = total body clearance; Cmax = maximum observed plasma concentration; Css-avg = average plasma concentration over a dosing interval at steady state; Ctrough = trough observed plasma concentrations; T-HALF = apparent terminal half-life; T-HALFeff = effective elimination half-life; Tmax = time of maximum observed plasma concentration; Vss = volume of distribution at steady-state; Vz = volume of distribution of the elimination phase.

### 10.3.3.1 Exploratory Population PK and Exposure Response Analyses

BMS-986277 alone or in combination with nivolumab concentration data and baseline characteristic data from this study may be combined with data from other studies for an integrated PPK analysis. The PPK analysis can be used to understand BMS-986277 PK in monotherapy and combination therapy with nivolumab, to explore effects of baseline characteristics on BMS-986277 PK, and to understand if BMS-986277 affects the PK of nivolumab. These analyses may be described in a separate analysis plan, and the results of these analyses may be presented in a separate report.

BMS-986277 alone or in combination with nivolumab concentration and clinical and biomarker data (eg, baseline characteristic, biomarker response, clinical response, and/or safety data) from this study may be analyzed separately or combined with data from other studies to understand exposure-response relationships following monotherapy and combination therapy. Exposure-response analyses may be conducted to explore relationships between BMS-986277 alone or in combination with nivolumab PK parameters (eg, AUC, Cmax, etc) and clinical responses and/or safety effects following treatment administration. Details of these analyses may be described in a separate analysis plan, and the results of these analyses may be presented in a separate report.

### 10.3.4 Immunogenicity Analyses

All IMG analyses will be performed on the IMG population. Each endpoint will be summarized for BMS-986277 and nivolumab separately, pending availability of evaluable data. Details of the IMG data analysis, including ADA titers, will be provided in the Statistical Analysis Plan.

Endpoint	Statistical Analysis Methods

Incidence of ADA
 
Baseline ADA-positive participant is defined as a participant who has an ADA-detected sample at baseline.a
 
ADA-positive participant is a participant with at least 1 ADA-positive sample relative to baseline after initiation of the treatment.
	
Frequency distribution of baseline ADA-positive participants and ADA-positive participants after initiation of the treatment

a Baseline sample is the last sample before initiation of the treatment. ADA, anti-drug antibody

[REDACTED]	[REDACTED]
[REDACTED]	[REDACTED]
[REDACTED]	[REDACTED]

[REDACTED]

[REDACTED]	[REDACTED]
[REDACTED]	[REDACTED]
[REDACTED]	[REDACTED]

### 10.3.7 Assay Performance Analyses

Assay performance analysis will be performed on the biomarker and response evaluable population. This analysis is only applicable to the Combination Dose Escalation (Part 2) and Cohort Expansion (Part 3 Cohorts 1-2).

A logistic regression model will be used to explore the association between a diagnostic assay and response to BMS-986277 in combination with nivolumab. This model may be adjusted for BMS-986277 dose and/or biomarker level and/or indication. The model will inform a biomarker cutpoint(s), along with the efficacy achieved for participants at each cutpoint and the prevalence rate of participants at each cutpoint. The cutpoint performance characteristics will be evaluated with the following endpoints.

Endpoint	Statistical Analysis Methods
Sensitivity and specificity PPV and NPV TPR and FPR	Logistic regression model Receiver Operating Characteristics (ROC) plot and corresponding AUC Plot of estimated TPR, FPR, PPV, NPV, and prevalence rate of participants versus biomarker level or the predicted probability of response from the full model (x-axis)

Abbreviations: FPR = false positive rate; NPV = negative predictive value; PPV = positive predictive value; TPR = true positive rate.

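### Protocol 10.3.7 evaluates its biomarker model and cutpoint in the same participants used to derive them, and states no correction for optimism

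*Protocol*

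**What the plan says.** Protocol 10.3.7 sets the analysis set: "Assay performance analysis will be performed on the biomarker and response evaluable population". It covers Part 2 and Part 3 Cohorts 1-2. The aim is exploratory: "A logistic regression model will be used to explore the association between a diagnostic assay and response to BMS-986277 in combination with nivolumab". Adjustment is optional: "This model may be adjusted for BMS-986277 dose and/or biomarker level and/or indication". On the output: "The model will inform a biomarker cutpoint(s), along with the efficacy achieved for participants at each cutpoint".

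Cutpoint performance is then described by sensitivity, specificity, PPV, NPV, TPR, FPR and an ROC plot with its AUC. The rates may be plotted against the biomarker level or against "the predicted probability of response from the full model". The section names no hold-out set, cross-validation, bootstrap or other correction. It also attaches no AUC threshold, test or decision.

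Protocol 10.3.8 sends further exploratory analyses to the SAP, and SAP section 1 gives the SAP precedence over the protocol's statistical text. The SAP refers to its sections 5.3.1 to 5.3.3, which are not in the public copy.

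**The concern.** An AUC of 0.5 means no information for a score fixed in advance. For a score whose coefficients were estimated from the same participants, the expected AUC under no association is above 0.5, and it rises with the number of fitted terms. Likewise, a cutpoint chosen because it separates responders well in these data will show better sensitivity and specificity here than elsewhere.

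At stake is what the reader concludes about the assay. Protocol section 3 says the Part 3 cohorts are meant to inform future studies, and 10.3.9 allows interim biomarker results to feed programme decisions and publications. Uncorrected figures would make the assay and its cutpoint look better than they would prove in the next study.

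**Working it through.** **Inputs from the documents.**
- Sample size: "The sample size for Cohort 1 and 2 is up to 40 participants per cohort" (Protocol 10.1.2), so 40 + 40 = 80. Part 2 adds up to 36 (10.1.1.2), giving at most 80 + 36 = 116.
- Response rates: uninteresting rates of 6% and 20% in the low and mid CD8 cohorts (10.1.2), which average (6 + 20)/2 = 13%. Target rates of 20% and 40% (10.1.2.1 and 10.1.2.2) average 30%. A rate of 20% lies between.
- Indications: two or more per cohort (10.1.2), with enrolment possibly focused on two per cohort (5.1.3). Two cohorts could therefore hold four. Six tumour types are admitted in Part 2 (6.1).

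**The plan's own figures.** Section 10.3.7 gives none. The Part 3 rules that supply the sample sizes and rates reproduce by exact binomial tails:
- Cohort 1: P(X ≥ 5 | 35, 0.06) = 0.056 and P(X ≥ 5 | 35, 0.20) = 0.857.
- Cohort 2: P(X ≥ 11 | 33, 0.20) = 0.051 and P(X ≥ 11 | 33, 0.40) = 0.831.

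**Information per fitted term.** Six indications add 5 coefficients, or 6 with the biomarker. Expected responders run from 80 × 0.13 = 10.4 to 116 × 0.30 = 34.8. That is 10.4/6 = 1.7 to 34.8/6 = 5.8 responders per coefficient, so substantial optimism is expected.

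**Simulation with no association.** Response is independent of every covariate. A logistic model is fitted, and the AUC is computed in the same data as the share of responder/non-responder pairs in which the responder has the higher fitted score, ties counting half. Assumptions not in the documents: biomarker log-uniform, half below 2% and half from 2% to 20%; indications equally frequent. There were 800 to 1000 trials per setting. At N = 116, rate 20% and six indications, the 10–90% range of 0.596 to 0.719 implies an SD of about 0.123/2.56 = 0.048, so the Monte Carlo error of that mean is about 0.048/√800 = 0.002.

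Mean apparent AUC:

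| N | Response rate | Biomarker only | + 2 indications | + 4 | + 6 |
|---|---|---|---|---|---|
| 80 | 13% | 0.58 | 0.62 | 0.68 | 0.73 |
| 80 | 20% | 0.56 | 0.60 | 0.65 | 0.69 |
| 80 | 30% | 0.56 | 0.59 | 0.63 | 0.66 |
| 116 | 13% | 0.57 | 0.60 | 0.65 | 0.69 |
| 116 | 20% | 0.56 | 0.58 | 0.63 | 0.66 |
| 116 | 30% | 0.55 | 0.57 | 0.61 | 0.64 |

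A dose term raises these a little: at N = 116 with six indications they become 0.70, 0.67 and 0.65. Allowing for it, the ranges are about 0.57–0.65 with two indications and about 0.61–0.74 with four to six. The exact upper ends depend on how many participants received a second dose.

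Fitted models for the biomarker alone and with two or six indications were also scored on new participants with no association. Their mean AUC was 0.498 to 0.503.

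**Where the AUC excess comes from.** At N = 80 and 20%, the excess over 0.50 is 0.06 for the biomarker alone and 0.19 with six indications. The indication terms account for 0.19 − 0.06 = 0.13 of it. The smaller part arises because the data also choose the direction of the biomarker effect.

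**Cutpoint.** The plan names no selection rule. As an illustration, maximising sensitivity + specificity − 1 for the biomarker alone at N = 80 and 20% gives mean sensitivity 0.65 and specificity 0.58. The index is 0.65 + 0.58 − 1 = 0.23, when its true value is 0. At N = 116 it averages 0.17 to 0.23 if the direction is fitted and 0.11 to 0.17 if it is fixed beforehand.

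**The case against.** Much can be said for the plan. The analysis is exploratory, drives no decision in this trial and does not name CD8. The 2% and 20% CD8 cutoffs that assign cohorts are fixed in advance from a nivolumab-only study (SAP 6.3). Adjustment is optional, and performance may be plotted against the biomarker level itself. TPR and FPR at a cutpoint fixed in advance, read off such a plot, carry no optimism. Validation may be specified in SAP text that is not public. All of this stands, and it limits the point to a reporting improvement in 10.3.7.

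A reader might infer three stronger things that the documents do not support:
- That the plan will report an AUC well above 0.6 when there is no signal. That needs several indication terms; the biomarker alone averages 0.55–0.58.
- That the assay would look predictive in most trials. The plan sets no threshold and makes no comparison with 0.5, so this depends on a criterion brought from outside. Above 0.60, the share under no association is 9–30% for the biomarker alone and 53–99% with four to six indications. Above 0.70, most settings do not reach half of trials.
- That choosing the cutpoint inflates the AUC. It cannot, because the AUC summarises all cutpoints. It inflates the sensitivity and specificity of the chosen cutpoint.

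Nor is no association the only plausible state. With equal cohorts responding at 6% and 20%, the low/mid split alone has sensitivity 0.20/0.26 = 0.77, specificity 0.94/1.74 = 0.54 and AUC of about (0.77 + 0.54)/2 = 0.65. This also shows why correction helps: an apparent 0.65 could reflect that contrast or nothing at all.

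**Conclusion.** The point holds for Protocol 10.3.7 as written. Model, cutpoint and performance come from one set of participants, with no internal validation stated there. Under no association the apparent AUC exceeds the value in new participants by about 0.05–0.08 for the biomarker alone, 0.07–0.15 with two indications and 0.11–0.24 with four to six. These sizes rest on the assumed biomarker distribution, equal indication frequencies, 80 to 116 evaluable participants and 13% to 30% response.

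In an indication-adjusted model most of the excess belongs to tumour type, so that AUC does not measure the assay. The cutpoint figures illustrate the mechanism under one selection rule; they do not predict what the plan's unstated rule would give. This is a cheap improvement to an exploratory analysis. Whether the SAP already covers it cannot be determined from the public text.

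**What to change.** In Protocol 10.3.7 and the matching SAP section, state that:
- AUC, TPR, FPR, PPV and NPV are reported after bootstrap optimism correction or repeated cross-validation, with model fitting and cutpoint selection both repeated in every resample.
- Apparent values appear only beside the corrected ones.
- The assay's contribution is the gain in corrected AUC from adding it to a model with dose and indication only.

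If the SAP already specifies this, a cross-reference from 10.3.7 is enough. With perhaps 10 responders, some resamples will contain indications without any, so the text should say how such fits are handled.

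The cost is a few lines of text and code, with no new data, participants or design change. The downside is slightly more analysis work and less favourable reported performance.

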### **10.3.8 Other Analyses**

Further exploratory analyses not specified here will be described in the Statistical Analysis Plan, which will be finalized before database lock and may be presented separately from the main clinical study report.

### **10.3.9 Interim Analyses**

Administrative interim analyses on safety, efficacy, PK, IMG, and selected biomarkers may be performed at various times prior to the final analysis in order to inform subsequent parts of the study, facilitate program decisions, and to support scientific publications or presentations. The timing of these database locks (and their associated last patient last visits [LPLVs]) and analyses will depend on the rate in which the data matures. No formal inferences requiring any adjustment to statistical significance level will be performed

